The overall Specific Aim of this proposal is to determine the effect of opioid taper on pain sensitivity in patients with chronic pain. Specifically, in a well-characterized sample of men and women with chronic neuropathic pain and receiving high-dose opioid therapy (200mg morphine equivalents/day [MED]), experimental pain responses will be serially described over the course of an individualized opioid taper to a safer dose of 90mg MED for up to 12 months. Changes will be inspected within-subject over time, and pain perception will be measured with two valid and reliable experimental pain induction techniques commonly used to measure OIH (cold-pressor, quantitative sensory testing); in addition, related functional improvements and subject-level predictors of response will be described. Hypothesis 1. Subjects undergoing opioid taper will have improved pain responses over time compared to within-subject baseline as measured by cold-pressor and quantitative sensory pain testing. Hypothesis 2. Improvements in experimental pain responses will be positively related to improved functional outcomes compared to within-subject baseline as measured by the PROMIS physical, mental and social health measures. Hypothesis 3. Degree of improvement in experimental pain responses related to opioid taper will be predicted by demographic, pain, and opioid use history characteristics of the subject. Data showing that pain perception improves as opioids are withdrawn would provide an evidence-based, mechanistic rationale for opioid taper in patients with chronic pain and have the potential to support a sea-change in opioid prescription practices. In that ongoing opioid therapy brings with it significant health risks for the patient and the community, it is critical that empirical evidence of its efficacy be demonstrated to balance the benefits with the risks of adverse events, potential misuse and abuse, and patient safety.

Primary outcome variable(s)

The primary dependent variable, pain perception, will be measured using two highly reliable and valid pain induction techniques, the cold-pressor test (CPT) and quantitative sensory testing (QST), employing procedures consistent with those described in the literature. Order of pain testing will vary, and three aspects of the pain response will be captured at each study session: evoked pain; temporal summation; and conditioned pain modulation, which map on to the hypothesized peripheral, spinal and supra-spinal mechanisms of OIH.

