
Study Design

Phase*

Not applicable

Design

A prospective time-series survey design will be utilized to measure the experimental (CPT and QST) pain responses of chronic pain patients on high-dose opioid therapy (200mg MED) prior to and then regularly during and following a voluntary opioid taper. Data will be collected weekly during the active taper period; once the subject has reached a stable maintenance dose (90 MED), assessments will occur monthly until month 12. Because our previous work has shown stability in pain responses in patients on

high-dose opioid therapy over time (6 months), and the clinical imperative of tapering patients to safer doses, a control group of patients maintained on high-dose therapy is not included. Consistent with expert opinion in the field, a longitudinal within-subject design is planned.

Study duration

The overall duration of the study is two years, during which time all subjects will be enrolled and complete the study. Data will be collected weekly during the active taper period; once the subject has reached a stable maintenance dose (less than or equal to 90 MED), assessments will occur monthly until month 12. If funded, the study would begin Oct 1, 2018.

Resources necessary for human research protection

Describe research staff and justify that the staff are adequate in number and qualifications to conduct the research. Describe how you will ensure that all staff assisting with the research are adequately informed about the protocol and their research related duties. Please allow adequate time for the researchers to conduct and complete the research. Please confirm that there are adequate facilities for the research.

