The study will be staff by a 55% FTE Project Director assisted by two part time graduate student research assistants (10hr/week) who will assist with pain testing and data collection. The project director is well-trained and experienced in all study procedures and human subjects research; with the PI, he will ensure the research assistants are trained and qualified to conduct research. Weekly research meetings between the investigators and study staff will occur to ensure staff are adequately informed about the protocol and their research-related duties. The PI has her own locking office space ([name], approximately 170 square feet). All faculty offices come equipped with locked filing cabinets, bookshelves, desk, minimum 4 GHz computer with HP printer, Windows XP service pack 3 operating system, Microsoft Office Professional (Word, Excel, PowerPoint, Access), SPSS or SAS statistical analysis software, and e-mail and internet access. With the same resources, an adjacent cubicle space is dedicated to the study research assistant. NHS copier, printer, fax and scanner facilities are available on each floor. Research visits will take place in a private office at the U Penn Pain Medicine clinic. The Penn Pain Medicine Center currently has eight clinical exam rooms, 7 administrative offices (office manager, physician, fellow, and resident offices), 5 support staff offices (2 billing/new patient coordinator, surgical coordinator, and research coordinator offices). There is a large clinical research area which houses the office of the clinical research coordinator along with 3 bays/exam locations for research patients. Study sessions will occur one of several small (10 ft x 15 ft) private examination rooms located onsite, complete with examining table, chair, bedside stand, desk, computer, and sink.

Characteristics of the Study Population

Target population

The sample will consist of 25 male and female adults with chronic neuropathic pain on opioid therapy and preparing to voluntarily undergo a prescribed opioid taper.

Subjects enrolled by Penn Researchers

25

Subjects enrolled by Collaborating Researchers

0

Accrual

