as a biological variable will be considered in all analyses. Statistical Analyses. The effect of opioid taper on changes in pain responses (CPT, QST), and functional outcomes (PROMIS domains) over time will be examined using longitudinal mixed-effects regression modeling, using general linear regression modeling with regularization as a function of baseline dose, end dose, and taper rate. These longitudinal profiles will be examined using a linear mixed effects framework with SAS Proc Mixed in which all available data collected during follow-up are used. Mixed models can account for the correlation between repeated measures and handle non-excessive missing data better than traditional models and allow for use of time-independent and time-dependent covariates. To assess patterns of attrition over time, a comparison of withdrawal rates and time to withdrawal will be included. Separate mixed effects regression models will be generated for each of the continuous outcome measures of interest (pain responses, functional outcomes). Random slopes and intercepts will be modeled to represent the participant-level deviation from the fixed-effect slope over time and intercept, respectively. Restricted maximum likelihood estimation will be used and the most appropriate covariance structure examined. Scores will be analyzed as repeated observations of the dependent variable, with mean-centered baseline outcome scores serving as a covariate. Other predictor variables will include baseline demographic characteristics of the patient, severity and chronicity of pain suffered, and opioid use history. Baseline measures will be analyzed as time-independent covariates. The Akaike information criterion will be used to evaluate overall model fit and to select the best-fitting longitudinal change pattern. .

The following documents are currently attached to this item:

There are no documents attached for this item.

Data confidentiality

- x Paper-based records will be kept in a secure location and only be accessible to personnel involved in the study.**
- x Computer-based files will only be made available to personnel involved in the study through the use of access privileges and passwords.**
- x Prior to access to any study-related information, personnel will be required to sign statements agreeing to protect the security and confidentiality of identifiable information.**
- x Wherever feasible, identifiers will be removed from study-related information.**

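### With baseline entered only as a mean-centred covariate, the one-group model does not directly estimate change from baseline, and comparing its fitted follow-up level with the baseline mean understates the standard error

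*Combined protocol and SAP*

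**What the plan says.** Hypothesis 1 (Objectives, Overall objectives) reads: "Subjects undergoing opioid taper will have improved pain responses over time compared to within-subject baseline". Under Study Design, Design, the protocol states that "a control group of patients maintained on high-dose therapy is not included" and that "a longitudinal within-subject design is planned". The sample size is given under Target population: "The sample will consist of 25 male and female adults with chronic neuropathic pain on opioid therapy".

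Under Analysis Plan, Statistical Analyses, the pain and PROMIS outcomes each get a REML linear mixed model "in which all available data collected during follow-up are used". Its random part is described thus: "Random slopes and intercepts will be modeled to represent the participant-level deviation from the fixed-effect slope over time and intercept, respectively". Baseline is handled in two sentences: "Scores will be analyzed as repeated observations of the dependent variable, with mean-centered baseline outcome scores serving as a covariate" and "Baseline measures will be analyzed as time-independent covariates".

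The section does not say that the baseline session is also a time-0 response. It names no contrast that tests follow-up against baseline, and it gives no standard error for such a contrast.

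**The concern.** Adjusting for baseline as a covariate works well when groups are compared, because error in the common baseline mean cancels in the difference. Here there is one group, and the comparator is baseline itself, so nothing cancels.

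Centring the covariate makes the intercept the expected follow-up score of a subject with an average baseline. Subtracting the sample mean baseline gives the right point estimate of mean change. The model's standard error, however, treats the baseline mean as a known constant when it is an average of 25 noisy measurements. Naming this contrast and taking its error from the same model would not help, because the missing term is not in the model. Using change scores as the response with the same centred covariate gives the same too-small standard error.

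At stake is the main claim of an uncontrolled study: that pain responses improved from baseline.

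**Working it through.** **The plan's own figures.** The documents give no standard error, interval width or error rate for change from baseline, so there is no figure to reproduce. The power statement under Accrual gives no numerical effect size, and this point does not rest on it.

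**Inputs.**
- From the documents: 25 subjects, one group, 30 to 40 visits (Subject compensation), and a Bonferroni level of 0.05/4 = 0.0125 (Accrual).
- Assumed, because not given: single-session reliability r (the correlation between baseline and a follow-up score) of 0.6 to 0.9, equal score SD s at all sessions, and a between-subject SD of slopes of 0 to 0.10 score SD per month.

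**Standard errors with no slope variation.** For the average of k follow-up sessions and n subjects:
- true variance of mean change: s²(1 − r)(1 + 1/k)/n
- variance reported by the baseline-adjusted model: s²(1 − r)(r + 1/k)/n
- ratio of model SE to true SE: sqrt[(r + 1/k)/(1 + 1/k)]

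For one visit the ratio is sqrt[(1 + r)/2]; for many visits it tends to sqrt(r). The missing variance is (1 − b)² × var(baseline)/n, where b is the baseline coefficient. It cannot be negative, so omitting it never makes the standard error too large. As a worked case, r = 0.6 and k = 30 give sqrt(0.6333/1.0333) = 0.783.

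| r | SE ratio, 1 visit | SE ratio, mean of 30 | Rejection at nominal 5%, mean of 30 | Rejection at nominal 1.25%, mean of 30 |
|---|---|---|---|---|
| 0.6 | 0.894 | 0.783 | 11.8% | 4.5% |
| 0.7 | 0.922 | 0.842 | 9.4% | 3.2% |
| 0.8 | 0.949 | 0.898 | 7.7% | 2.3% |
| 0.9 | 0.975 | 0.950 | 6.3% | 1.8% |

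The rejection rates come from 40,000 simulated studies of 25 subjects with no true change. A separate run of 20,000 gave 11.9%, 9.3%, 7.3% and 6.2% at the 5% level. A paired change on the same data rejected 4.8–5.1% of the time.

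**With slopes that vary between subjects.** Rejection at nominal 5% for the fitted month-12 level minus the baseline mean (26 weekly plus 6 monthly sessions, 20,000 replicates, subject-level approximation):

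| r | Slope SD 0 | Slope SD 0.05 | Slope SD 0.10 |
|---|---|---|---|
| 0.6 | 10.2% | 7.4% | 6.0% |
| 0.7 | 8.7% | 6.7% | 5.8% |
| 0.8 | 7.0% | 5.7% | 5.1% |

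The excess shrinks because slope variance enters both standard errors. At slope SD 0.10 it adds (12 × 0.10)² = 1.44 (in units of s²) to the month-12 variance. At r = 0.6 the missing term is (1 − 0.6)² = 0.16, against a total of about 0.40 + 1.44 = 1.84. The SE ratio is then about sqrt(1 − 0.16/1.84) = 0.96. At month 6 with slope SD 0.10, the rates are 7.7%, 6.8% and 5.4% for r = 0.6, 0.7 and 0.8.

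**The time slope.** In the same setting, a test of the fixed slope rejected 4.7–5.1% of the time, so its standard error is sound. A slope within follow-up is still not a comparison with baseline: an early change followed by a plateau could leave little slope.

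**The case against.** The strongest reply is that the plan never states the faulty comparison. Its model describes change over time through a fixed slope and lets an information criterion choose the shape, and the slope test holds its size. Sessions are weekly during the taper. At the 10–15% per month quoted under Procedures, dose has fallen only about 2–4% by week 1, so a trend that starts there is close to change from baseline. This stands in part. A reader might infer that the plan will declare improvement too often, or that setting the fitted level against the baseline mean is the model's only route to Hypothesis 1. The documents support neither, because no contrast is named. What remains is that the slope is not the comparison Hypothesis 1 states, and the level comparison has the wrong error.

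The plan also does not expressly exclude a baseline row from the response. The sentence making baseline measures time-independent covariates points the other way. If such a row exists, the same score is both outcome and covariate, which also needs correcting.

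The objection on size stands. The 12% figure needs low reliability and no slope variation. The plan models random slopes, tapers are individualised, and the protocol calls the tests highly reliable and cites stability over six months, though without a figure. All of this points toward the smaller excess.

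A reader might also infer that the baseline covariate does nothing useful. That goes too far: Hypothesis 3 compares subjects with one another, and baseline adjustment can sharpen those comparisons. Finally, Preliminary Analyses allows transformations or non-parametric tests for cold-pressor data, so this model may not be the final one for that outcome.

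**Conclusion.** The point holds as a mismatch between model and hypothesis. As written, the model either tests a trend within follow-up, which is valid but is not the stated comparison, or supports a comparison with the baseline mean whose standard error is too small.

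The direction is certain whenever the baseline coefficient differs from 1. The size is not, because reliability and slope variance are assumptions. It ranges from about 12% rejection at nominal 5% (average follow-up level, r = 0.6, no slope variation) to close to nominal (month 12, high reliability or widely varying slopes). The documents do not support a single inflated error rate for the trial. The change should be made because it is cheap and makes the model estimate what Hypothesis 1 states.

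**What to change.** In Analysis Plan, Statistical Analyses, replace the covariate sentence for the Hypothesis 1 pain models and the matching PROMIS change models. State that:
- the baseline session is the time-0 repeated observation in the response;
- the baseline score is not a covariate in these models, and the chosen time pattern runs from time 0;
- Hypothesis 1 is tested by a named follow-up minus time-0 contrast, with the follow-up time or average stated and the standard error taken from the model.

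A paired change, or adding (1 − b)² × var(baseline)/n to the squared standard error, also restores coverage. Baseline adjustment may stay in separate predictor models for Hypothesis 3.

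The cost is a few sentences of text and a second model specification per outcome; no new data or visits are needed. Intervals become somewhat wider. For a single follow-up visit the factor is sqrt[2/(1 + r)], which is 1.085 at r = 0.7 and 1.026 at r = 0.9.

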No other sites

Management of Information for Multi-Center Research

The following documents are currently attached to this item:

There are no documents attached for this item.

Protocol

Abstract

The US is in the midst of an epidemic of prescription drug abuse. According to the CDC, of the 52,404 opioid overdose deaths that occurred in 2015, almost 25% involved a prescription opioid, a number that has quadrupled since 1999. This public health crisis was fueled by well-intended efforts to better treat chronic pain, however, the use of opioids for ongoing pain is not an evidence-based intervention. In fact, outcomes are often poorer for patients on opioids, with counterintuitive improvements appreciated when opioids are tapered. An oft-cited but untested explanation for this finding is opioid-induced hyperalgesia (OIH), or increased pain sensitivity secondary to ongoing opioid use. Unknown is the degree to which OIH contributes to the pain experience or how opioid taper might improve pain sensitivity. Proposed is an observational pilot designed to measure the effect of opioid taper on pain perception in patients with chronic pain. In a well-characterized sample of pain patients on high-dose opioid therapy, we will examine responses to experimental pain (cold-pressor, quantitative sensory) during a prescribed opioid taper. Responses will be measured at weekly intervals over the course of the taper, followed by monthly intervals up to 12 months. In addition to characterizing pain perception over time, functional outcomes and variables related to the patient, chronic pain condition, and opioid therapy will be evaluated. It is anticipated that study findings will explicate the role opioid therapy plays in the pain experience of chronic pain patients, thereby providing evidence-based guidance for treatment.

Objectives

Overall objectives

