
The following documents are currently attached to this item:

Procedures (datacollectionschedule.docx)

Procedures (appacoldpressortestinginstructionsandscrip.docx)

Procedures (appbquantitativesensorytestinginstructionsandscrip.docx)

Deception

Does your project use deception?

No

International Research

Are you conducting research outside of the United States?

No

Analysis Plan

Preliminary Analyses. Preliminary analyses will include generating descriptive statistics for all baseline measures to characterize the sample, including measures of central tendency and variation for continuous variables; for dichotomous/categorical variables, measures will include frequencies and percentages. Distributional properties will be examined to determine if variance stabilizing or normalizing transformations are required. Non-inferential interim analyses will be performed to ensure data collection and archiving procedures are operating correctly. Outliers will be assessed by visual inspection and checked for accuracy. Normality will be assessed using Shapiro-Wilk tests; should violations emerge (i.e., cold-pressor data are anticipated to be bimodal), transformations or non-parametric tests will be used. Due to known differences in pain responses between men and women, sex

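### AIC is to choose the time shape while REML is the only likelihood method named; the plan should specify ML fits for that comparison

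*Combined protocol and SAP*

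**What the plan says.** The relevant text is in the Analysis Plan, under Statistical Analyses.

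- Software: "These longitudinal profiles will be examined using a linear mixed effects framework with SAS Proc Mixed".
- Where time enters: "Random slopes and intercepts will be modeled to represent the participant-level deviation from the fixed-effect slope over time and intercept, respectively". The average course over time is therefore a fixed effect.
- Estimation: "Restricted maximum likelihood estimation will be used and the most appropriate covariance structure examined". No maximum likelihood (ML) fit is mentioned anywhere.
- Choice of shape: "The Akaike information criterion will be used to evaluate overall model fit and to select the best-fitting longitudinal change pattern". The candidate patterns and the time unit are not given.

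Hypothesis 1, in the Objectives, is the claim that the selected shape serves: "Subjects undergoing opioid taper will have improved pain responses over time compared to within-subject baseline". Under Study Design, data are "collected weekly during the active taper period; once the subject has reached a stable maintenance dose (90 MED), assessments will occur monthly", so weeks and months are both natural units for time.

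**The concern.** An analyst who follows the plan literally fits each candidate shape by REML and takes the AIC that is printed. Candidate shapes such as linear, quadratic or piecewise time differ in their fixed terms. The REML criterion contains a term that depends on the fixed-effects design matrix, so its values for different shapes are not on a common scale. REML-AIC is suitable for choosing a covariance structure when the fixed effects are the same in every model.

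The plan's own logic makes curvature plausible. Dose falls during the taper and is then held, so a response that tracks dose would bend near the end of taper. If the selection rule wrongly keeps a straight line, the change reported around that time is too small.

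**Working it through.** The plan gives no figure for this step, so there is none to reproduce.

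**1. Why the REML values are not comparable.** Minus twice the REML log-likelihood contains + log|X'V⁻¹X|, where X holds the fixed effects. Some versions also subtract log|X'X|. Changing the fixed time terms changes X, and with it this part of the criterion, apart from any change in fit.

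**2. Exact effect of the time unit when log|X'X| is omitted.** Multiply time by c. Log|X'V⁻¹X| then rises by 2 ln(c) for each power of time in the model.
- Linear: 2 ln(c).
- Quadratic: 2 ln(c) + 4 ln(c) = 6 ln(c).
- Quadratic minus linear: 4 ln(c).

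From months to weeks, c = 30.44/7 = 4.349 and ln(c) = 1.470, so the shift is 4 × 1.470 = 5.88 AIC units, whatever the data. Piecewise linear minus linear shifts by 2 × 1.470 = 2.94. Direct refits in both units gave 5.879 and 2.940. The ML difference does not move.

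**3. One simulated data set (0.5 SD change), AIC quadratic minus linear.** Negative values select the curve.

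| Criterion | Months | Weeks |
|---|---|---|
| REML without log\|X'X\| | −2.55 (curve) | +3.33 (line) |
| REML with log\|X'X\| | −13.93 (curve) | −13.93 (curve) |
| ML | −11.19 (curve) | −11.19 (curve) |

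The first row differs by 3.33 + 2.55 = 5.88, as in step 2.

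**4. Simulation inputs.**
- From the documents: 25 subjects; taper from 200 to 90 MED at 10–15% per month (Procedures, Standard of Care); weekly then monthly visits to month 12. Compounded, the taper lasts ln(200/90)/−ln(0.85) = 4.9 to ln(200/90)/−ln(0.90) = 7.6 months. This gives about 32 visits per subject.
- Assumed: random intercept SD 0.8, random slope SD 0.03 per month, residual SD 0.6 (0.8² + 0.6² = 1, so effects are in SD units); centred baseline score as covariate; Gaussian data; no dropout; change proportional to dose reduction and flat after taper.
- Candidate shapes, also assumed: linear and quadratic.
- Penalty: ML-AIC counts the fixed effects; REML-AIC counts covariance parameters only and omits log|X'X|. Counting fixed effects there would add 2 to the difference and favour the line further.

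**5. Share of data sets in which the curve was chosen, 0.5 SD change** (80 to 150 runs per setting; ranges span repeated simulations with small schedule differences):

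| ML-AIC | REML-AIC, months | REML-AIC, weeks |
|---|---|---|
| about 97–99% | about 53–66% | about 17–23% |

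**6. What the shape does to the estimate, 0.5 SD change.**
- Month 6, from fitted time 0: line about 0.26 SD, quadratic 0.46–0.48, truth about 0.48.
- Month 12, from fitted time 0: line 0.51, quadratic 0.45, truth 0.50.

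**7. What it does to the test.** The Accrual section sets alpha at 0.05/4 = 0.0125. At that level the result differed between the REML-AIC and ML-AIC choices in 0.7% of data sets (month 6) and 4.7% (month 12) at 0.5 SD, and in none at 0.8 SD. The plan names no contrast, so these months are examples.

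**8. No true change.** ML-AIC picked a false curve in roughly 12–24% of data sets. REML-AIC as defined in step 4 picked almost none.

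**9. If the software includes log|X'X|.** Unit dependence disappears. Over a wider set of variances and effects (20 settings, 400 runs each), REML-AIC without a fixed-effect penalty then chose a curve in 94–100% of no-change data sets. With the penalty, it disagreed with ML-AIC in 0–20% of no-change data sets and 0–23% of those with a change.

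**The case against.** The strongest reply is that the plan contains no stated error. REML is attached to estimation and covariance structure, and the AIC sentence names no likelihood. An analyst who compared shapes by ML and reported REML estimates would not contradict the text. That is correct: the REML link is an inference. It still stands as the natural reading, because REML is the only method named and nothing sends the analyst to ML.

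The quadratic and piecewise shapes are not in the documents either. The selection rates depend on them, but the incomparability applies to any candidates with different fixed time terms.

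ML-AIC is not the truth. With no change, the disagreement between the two criteria consists of ML-AIC picking a false curve (step 8), so those cases are no evidence of harm from REML-AIC. This stands, and it is why the selection needs an exploratory label.

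Two stronger readings are tempting. One is that the Hypothesis 1 test is invalid or its type I error inflated. The documents do not support this: no inflation was shown, and at the plan's own alpha the result seldom changes in the moderate-to-large effect range that the Accrual section expects. The other is that choosing a shape from the data is itself improper. The Abstract says "Proposed is an observational pilot designed to measure the effect of opioid taper on pain perception in patients with chronic pain", and in a pilot such a choice is reasonable if it is labelled.

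**Conclusion.** The point holds as a gap that leads, on the natural reading, to an invalid comparison. The 5.88-unit shift is exact but applies only if the REML likelihood omits log|X'X|, which the plan does not settle. If the term is included, the unit no longer matters, but the comparison across shapes is still not valid.

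The practical consequence is a tendency to miss a bend and so understate the change around the end of taper: about 0.26 against a true 0.48 SD at month 6 in the case studied. The month-12 estimate from fitted time 0 and the test conclusions are little affected.

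The rates rest on assumed variances, an assumed dose-following response, Gaussian outcomes and about 32 visits. They do not cover the PROMIS outcomes, which are monthly, or the plan's further covariates. Nor do they cover the cold-pressor outcome, where "cold-pressor data are anticipated to be bimodal" and transformations or non-parametric tests are allowed. Confidence is moderate.

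**What to change.** Add one or two sentences to the Analysis Plan stating that:

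- the candidate time shapes, listed with the time unit, are compared by AIC from ML fits that count the fixed effects;
- the chosen model is refitted by REML for estimates and inference;
- REML-AIC is used only to choose the covariance structure, with the same fixed effects in every model compared;
- the shape selection is exploratory.

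The cost is one extra ML fit per candidate shape. No new data are needed, and sample size, alpha and power are unchanged. The drawback is that ML-AIC sometimes selects a curve when there is none.
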